5.1.3 Pooling of Centers

As sample size per center will be small, all the centers will be pooled together for the analysis.

5.1.4 Adjustments for Covariates

Appropriate analysis of covariance (ANCOVA) will be conducted with treatment and weight group as the main factors and the baseline value as the covariate.

5.1.5 Multiple Comparisons/Multiplicity

Pairwise comparisons (Treatment 1 vs. Treatment 2, Treatment 2 vs. Treatment 3, and Treatment 3 vs. Treatment 4) will be performed but without adjustment for multiple comparisons.

5.1.6 Examination of Subgroups

Subgroup analyses for efficacy will be performed on categories of the following measures:

- Gender
- Race
- Weight

for the ITT population. Subgroup analysis will comprise of summary statistics only, i.e. there will be no statistical testing.

5.1.7 Methods for Handling Dropouts or Missing Data

Subjects who discontinue the study without post-randomization scores will not be included in the analysis of efficacy variables. Last observation carried forward (LOCF) technique will be used in the efficacy analysis for subjects who discontinue the study with post-randomization scores.

5.2 PRIMARY EFFICACY ANALYSIS

5.2.1 Analysis of NCBRF-TIQ Conduct Problem Subscale

The NCBRF-TIQ Conduct Problem subscale score is the primary efficacy variable. To assess the effect of SPN-810 in reducing persistent serious conduct problems as measured by the conduct problem subscale of the NCBRF-TIQ after 6 weeks of maintenance treatment, the following primary efficacy analysis (Section 5.2.2) will be conducted.

5.2.2 Results of Primary Efficacy Analysis

The changes from baseline in the NCBRF-TIQ conduct problem subscale scores at each post-baseline visit and endpoint will be compared among treatment groups using Kruskal-Wallis test (for the overall comparisons) and Wilcoxon rank-sum test (for the pairwise comparisons of Treatment 1 vs. Treatment 2, Treatment 2 vs. Treatment 3, and Treatment 3 vs. Treatment 4) for the ITT population. The Hodges-Lehmann estimators and associated 95% confidence intervals will be calculated for the median differences between Treatment 1 and Treatment 2, Treatment 2 and Treatment 3, and Treatment 3 and Treatment 4 (Hollander M, 1999). Table 5.2.2.1 provides the primary efficacy results for overall and pairwise comparisons for NCBRF-TIQ conduct problem subscale for the ITT population. Table 5.2.2.2 provides the summary statistics for NCBEF-TIQ conduct problem subscale for the restricted ITT population.

Listing 5.2.2.1 provides NCBRF-TIQ conduct problem subscale data for the ITT population.

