3. DESIGN OF THE STUDY

3.1 STUDY DESIGN

This will be a randomized, multicenter, parallel group, dose-ranging safety and tolerability study in children with ADHD and persistent serious conduct problems. The target subjects are healthy male or female children aged 6 to 12 years, inclusive, with a diagnosis of ADHD with persistent serious conduct problems. To determine eligibility for the study, subjects will undergo an initial screening visit. Seventy-two subjects will be randomized in the study; assuming a 17% dropout rate, it is anticipated that 60 subjects will complete the study.

[figure not shown]
The study will consist of a Screening Period (within 28 days prior to the first dose administration), a Titration Period of 2 to 5 weeks, a Maintenance Period of 6 weeks, and a Safety Follow-up, which will be performed 30 days after the final study visit. The total subject duration in the study will be 16 to 19 weeks depending on the treatment group assignment. The total study duration is anticipated to be 15.5 months.

A total of 72 subjects will be randomized based on weight at baseline, to 1 of 4 treatment groups. A dose titration schedule will be followed (Table 1), where dosing for subjects < 30kg will be initiated at 1.67mg/day and dosing for subjects \geq 30kg or more will be initiated at 3.34mg/day. The titration schedule will be followed until the target dose (Treatment 1, 2, 3, or 4) is reached. Subjects will remain at the target dose for 6 weeks.

Table 1. Dose Titration Schedules (mg/day)

Week	1	2	3	4	5	6
Treatment Weight	Titration	Titration	Titration or Treatment 1	Titration or Treatment 2	Titration or Treatment 3	Treatment 4
< 30kg	1.67 (1.67mg qhs)	3.34 (1.67mg bid)	5 (1.67mg tid)	10 (3.33mg tid)	15 (5mg tid)	20 (6.67mg tid)
≥ 30kg	3.34 (1.67mg bid)	5 (1.67mg tid)	10 (3.33mg tid)	20 (6.67mg tid)	30 (10mg tid)	40 (13.33mg tid)

A study schematic is presented below.

Following 2 weeks of titration, subjects randomized to Treatment 1 in each weight group will receive Maintenance Treatment 1 (5mg/day for children < 30kg and 10mg/day for children ≥ 30kg), while the remaining subjects will receive the same level of drug as a titration step to the next level (Maintenance Treatment 2: 10mg/day and 20mg/day) and so on until the final subjects in each weight group reach the highest doses (20mg/day and 40mg/day).

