3.1.1 Screening Period

A Screening Period will take place within 28 days prior to the first dose administration to determine subjects' eligibility to participate in the study. Prior to conducting any screening procedures, written informed consent/assent must be obtained from the parent or LAR, and subject (when required).

The NCBRF-TIQ will be administered to determine eligibility. The diagnosis of ADHD will be confirmed with the Schedule for Affective Disorders and Schizophrenia for School-aged Children—Present and Lifetime Versions (K-SADS-PL). The Introductory and Screen Interviews will be completed. The Screen Interview will determine which Supplements should be completed. Supplement 4 (Behavioral Disorders) must be completed to assess ADHD, ODD and CD. If an exclusionary diagnosis is confirmed, the remainder of the diagnostic will not be completed.

Other procedures to be performed will include the collection of medical history and demographic data, physical examination, collection of vital signs, height, and weight, electrocardiogram (ECG), blood collection for hematology and chemistry, urine collection for urinalysis, drug screen, and pregnancy test (for female subjects of menstruating age or ≥ 11 years old). The Kaufman Brief Intelligence Test, Second Edition (KBIT-2) should be administered if an IQ test has not been performed within the past 12 months prior to screening. Concomitant medication and AE information will be collected once informed consent/assent is obtained.

Unscheduled visits may be conducted at the discretion of the investigator throughout all study periods. The medical monitor should be notified promptly of any need for an unscheduled visit.

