3.3 RANDOMIZATION PROCEDURE

The randomization for this study will be managed centrally by an IVRS vendor; specific instructions to conduct subject randomization will be provided in a separate document to all investigational sites, along with site staff access to the system.

A randomization scheme will be generated using a pseudo-random number generator in a computer program. The method avoids bias by use of a chance mechanism. Within each weight group, the randomization scheme assigns Treatment 1, Treatment 2, Treatment 3, or Treatment 4 to each randomization number in a 1:1:1:1 ratio.

Upon admission to the study, subjects will be assigned a 4-digit screening number, in the order that they are entered. Subjects who subsequently meet all eligibility criteria will be assigned a 6-digit randomization number. The first 3 digits will refer to the site, and the last 3 will refer to the subject-specific number, which will be assigned according to the randomization scheme.

Once a randomization number has been assigned, no attempt should be made to use that number again, if, for example, a subject is withdrawn. All subjects are randomized only once.

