5.1.2 Treatment Comparisons

Statistical testing to compare treatment groups (overall and pairwise) will be performed for the ITT population only using appropriate statistical methods, as described in the efficacy subsections below. Dose-response relationship will be assessed based on a review of the results of the complete set of pairwise comparisons of Treatment 1 vs. Treatment 2, Treatment 2 vs. Treatment 3, and Treatment 3 vs. Treatment 4, without adjustment for

multiple testing. Given the small per-treatment group sample size for the study, the resulting p-values from the statistical testing will be used for descriptive purposes only (i.e., not for inferential purposes), primarily as an aid in the clinical interpretation of the efficacy results.

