5.3.1 Severity of Illness (CGI-S)

The changes from baseline in the CGI-S at each post-baseline visit and endpoint will be compared among treatment groups using Kruskal-Wallis test (for the overall comparisons) and Wilcoxon rank-sum test (for the pairwise comparisons of Treatment 1 vs. Treatment 2, Treatment 2 vs. Treatment 3, and Treatment 3 vs. Treatment 4) for the ITT population. The Hodges-Lehmann estimators and associated 95% confidence intervals will be calculated for the median differences between Treatment 1 and Treatment 2, Treatment 2 and Treatment 3, and Treatment 3 and Treatment 4. Table 5.3.1.1 provides secondary efficacy results for overall and pairwise comparisons for CGI-S for the ITT population. Table 5.3.1.2 provides summary statistics for CGI-S for restricted ITT population.

Listing 5.3.1.1 provides CGI-S data for the ITT population.

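### Treatment is randomised within weight group, but the main rank tests and Hodges-Lehmann intervals ignore weight group and baseline, which costs precision in most settings tested

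*SAP*

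**What the plan says.** Section 3.3: "Within each weight group, the randomization scheme assigns Treatment 1, Treatment 2, Treatment 3, or Treatment 4", in equal ratio. Section 3.1 and Table 1 give each treatment label a different daily dose in each weight group; for example, children "will receive Maintenance Treatment 1 (5mg/day for children < 30kg and 10mg/day for children ≥ 30kg".

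Section 5.2.2 compares changes in "conduct problem subscale scores at each post-baseline visit and endpoint will be compared among treatment groups using Kruskal-Wallis test", then uses Wilcoxon rank-sum tests and Hodges-Lehmann 95% intervals for 1 vs 2, 2 vs 3 and 3 vs 4. The secondary variables follow the same pattern; for CGI-S (5.3.1), "The changes from baseline in the CGI-S at each post-baseline visit and endpoint will be compared among treatment groups using Kruskal-Wallis test". CGI-I (5.3.2) is compared on actual scores. No weight stratum or baseline covariate appears in any of these sections.

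Section 5.1.4 says: "Appropriate analysis of covariance (ANCOVA) will be conducted with treatment and weight group as the main factors and the baseline value as the covariate". It names no variable. Section 5.5 carries out that model as a sensitivity analysis of the conduct problem subscale only, and mentions no adjacent-dose differences or intervals. Weight is also a subgroup factor in 5.1.6, but there "Subgroup analysis will comprise of summary statistics only, i.e. there will be no statistical testing".

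Section 5.1.2 makes p-values descriptive and adds: "Dose-response relationship will be assessed based on a review of the results of the complete set of pairwise comparisons".

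**The concern.** An analysis normally respects the factor used to stratify randomisation. Here the unstratified comparison also uses differences between children in different weight groups. For Treatment 1 vs 2, Table 1 makes those 5 vs 20 mg/day or 10 vs 10 mg/day, whereas the planned steps within a weight group are 5 vs 10 and 10 vs 20. Balanced allocation keeps this from biasing the result. If weight group is prognostic, though, the cross-group differences add noise and make the tests conservative.

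Subtracting baseline is also not the same as adjusting for it. A change score fixes the baseline slope at 1, which wastes precision when the true slope is lower. With small arms, the adjacent-dose intervals are what a reader will use to judge dose-response, so avoidable width matters even when p-values are descriptive.

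**Working it through.** **Inputs from the SAP.** 72 randomised to 4 arms: 72/4 = 18 per arm. With 17% dropout, 72 × 0.83 = 59.76, which reproduces the stated 60 completers, or 15 per arm. The SAP gives no power, SD, correlation or weight effect (3.2), so everything below is assumed and shown as a range.

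**Cross-weight differences.** Each adjacent Hodges-Lehmann estimate uses 18 × 18 = 324 differences. With an assumed 9/9 weight split, 2 × 9 × 9 = 162 of them cross weight groups. With 6/12, 2 × 6 × 12 = 144 do.

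**Formula for the baseline part.** Let follow-up SD be 1, baseline SD k and correlation r. The change score has variance 1 + k² − 2rk and the baseline-adjusted outcome 1 − r², so the variance ratio is (1 − r²)/(1 + k² − 2rk). An interval computed on residuals treats the two fitted terms (baseline and weight) as known. At 18 per arm this narrows it by a further √(66/68) = 0.985, which is not a real gain.

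**Simulated interval width, adjusted/planned** (18 per arm, normal data, no weight effect, 6,000 runs per setting; r = 0.3/0.5/0.7):

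| k | Variance ratio | Square root × 0.985 | Simulated |
|---|---|---|---|
| 1.0 | 0.650/0.750/0.850 | 0.794/0.853/0.908 | 0.793/0.852/0.909 |
| 0.8 | 0.784/0.893/0.981 | 0.873/0.931/0.976 | 0.871/0.930/0.976 |
| 0.6 | 0.910/0.987/0.981 | 0.940/0.979/0.976 | 0.940/0.979/0.975 |

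Formula and simulation agree within 0.002.

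**Full grid.** Three values of r, three of k, three residual shapes (normal, exponential, t3), weight effect 0 or 0.5 SD, and 18 or 15 per arm: 3 × 3 × 3 × 2 × 2 = 108 settings.
- Width ratio 0.64 to 1.00, below 0.97 in 90 of 108.
- Sampling SD ratio 0.633 to 1.035.
- Coverage 0.943–0.956 adjusted, 0.946–0.975 planned.
- Four-arm parametric ANCOVA against the planned interval: 0.75 to 1.28, wider in 43 of 108.

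**Bounded scales.** For an assumed 1–7 CGI-S, the width ratio was 0.78–1.01, and coverage of the mean difference was 0.92–0.95 adjusted against 0.88–0.93 planned. For an assumed nine-item SNAP-type mean, the width ratio was 0.85–0.97.

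**Weight stratification of the overall test** (18 per arm, 20,000 runs, normal data; 0.8 SD spread over four arms, r = 0.3/0.5/0.7):

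| Weight effect | Power, planned | Power, stratified | Null rejection, planned |
|---|---|---|---|
| 0 | 36/50/73% | 35/49/73% | 0.046–0.049 |
| 0.5 SD | 33/45/68% | 35/48/73% | 0.033–0.044 |
| 1.0 SD | 27/34/49% | 36/48/72% | 0.011–0.024 |

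The stratified test rejected a true null in 0.046–0.050 throughout.

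**The case against.** The SAP's methods are valid. Efficacy is a secondary objective, the sample size has no statistical basis and p-values are descriptive, so this could be called a preference about efficiency. The primary efficacy variable already has an ANCOVA with weight and baseline, section 4 plans summaries by weight category, and 5.1.4 can be read as covering every variable. Sections 5.1.2 and 5.1.5 call for the three pairs in general terms, and the table shells, which are separate documents, might show them for 5.5.

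The numerical objections are also fair. With weight groups balanced across arms, stratifying by weight alone does not sharpen the point estimate: the stratified/unstratified variance ratio was 1.02 to 1.13. At a 0.5 SD weight effect, the pairwise power gain at a 0.27 SD step is only 0.4 to 1.5 points, and nothing in the SAP says weight is prognostic. A count of grid settings is not a probability. Of the 27 settings at 18 per arm with no weight effect, 9 have ratios of 0.975 or more, 6 of them at k = 0.6. Restricted baseline spread is plausible for the primary variable, because "The NCBRF-TIQ will be administered to determine eligibility".

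These points limit the size and rule out ANCOVA as the lead analysis. They do not remove the gap. The SAP reports 95% intervals as well as p-values. Section 5.1.4 assigns no table or variable, and no section assigns an adjusted analysis to CGI-S or the SNAP-IV scores, or a weight-stratified one to CGI-I.

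**Conclusion.** The concern holds, as a loss of precision and calibration, not as bias or type I error inflation. Sections 5.1.4 and 5.5 do not contradict each other; 5.1.4 simply does not refer to 5.5 or say which variables it covers.

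There are two separate parts. Leaving out the baseline covariate widens the adjacent-dose intervals. With normal data, 18 per arm and no weight effect, the adjusted interval is about 9 to 21% narrower when baseline and follow-up SDs are equal, but only 2 to 6% narrower when baseline SD is 0.6 of follow-up SD. About 1.5 points of each figure comes from ignoring the fitted terms. Leaving out weight group makes the tests conservative if weight is prognostic: power falls by about 2 to 5 points at 0.5 SD and 9 to 23 points at 1.0 SD for the overall test, and hardly at all if weight has no effect.

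All sizes depend on the assumed correlations, spreads, weight effects and weight splits. The consequence is limited, but the change is cheap and worth making before database lock.

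**What to change.** Keep the rank-based framework and the planned results.

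1. In 5.2.2 and 5.3.1–5.3.5, stratify the tests by weight group: van Elteren for the three planned pairs, and for the overall test the Cochran-Mantel-Haenszel mean-score test on within-stratum ranks.
2. For the conduct problem subscale, CGI-S and the three SNAP-IV scores, report adjusted differences with 95% intervals for 1 vs 2, 2 vs 3 and 3 vs 4 beside the planned Hodges-Lehmann results. One way is to apply Hodges-Lehmann to the changes after subtracting baseline and weight-group terms fitted over all four arms.
3. In 5.5, state that the ANCOVA also reports these three differences with 95% intervals, as a supplement.
4. CGI-I has no baseline value, so it takes weight stratification only.
5. In 5.1.4, refer to 5.5 and list the variables covered.

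The cost is SAP wording and a few tables. If weight is not prognostic, van Elteren loses up to 1 point of power at a 0.27 SD step and about 2 points at 0.8 SD. The adjusted estimate assumes linearity and a common slope. In the least favourable of the 108 settings its sampling SD was 3.5% larger than the planned one. With slopes differing by ±0.2 between arms, its coverage stayed at 0.948–0.949.

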5.3 SECONDARY EFFICACY ANALYSES

For the analysis of secondary efficacy variables, no statistical adjustment to the level of significance will be made for multiple endpoints and/or multiple comparisons.

The secondary efficacy analyses for various secondary endpoints are as follows.

5.3.1 Severity of Illness (CGI-S)

The changes from baseline in the CGI-S at each post-baseline visit and endpoint will be compared among treatment groups using Kruskal-Wallis test (for the overall comparisons) and Wilcoxon rank-sum test (for the pairwise comparisons of Treatment 1 vs. Treatment 2, Treatment 2 vs. Treatment 3, and Treatment 3 vs. Treatment 4) for the ITT population. The Hodges-Lehmann estimators and associated 95% confidence intervals will be calculated for the median differences between Treatment 1 and Treatment 2, Treatment 2 and Treatment 3, and Treatment 3 and Treatment 4. Table 5.3.1.1 provides secondary efficacy results for overall and pairwise comparisons for CGI-S for the ITT population. Table 5.3.1.2 provides summary statistics for CGI-S for restricted ITT population.

Listing 5.3.1.1 provides CGI-S data for the ITT population.

5.3.2 Global Improvement (CGI-I)

Actual CGI-I scores at each post-baseline visit and endpoint will be compared among treatment groups using Kruskal-Wallis test (for the overall comparisons) and Wilcoxon rank-sum test (for the pairwise comparisons of Treatment 1 vs. Treatment 2, Treatment 2 vs. Treatment 3, and Treatment 3 vs. Treatment 4) for the ITT population. The Hodges-Lehmann estimators and associated 95% confidence intervals will be calculated for the median differences between Treatment 1 and Treatment 2, Treatment 2 and Treatment 3, and Treatment 3 and Treatment 4. Table 5.3.2.1 provides secondary efficacy results for overall and pairwise comparisons for CGI-I for the ITT population. Table 5.3.2.2 provides summary statistics for CGI-I for the restricted ITT population.

Listing 5.3.1.1 provides CGI-I data for the ITT population.

5.3.3 SNAP-IV Subscale: ADHD-Inattention

The changes from baseline in the ADHD-Inattention ratings at each post-baseline visit and endpoint will be compared among treatment groups using Kruskal-Wallis test (for the overall comparisons) and Wilcoxon rank-sum test (for the pairwise comparisons of Treatment 1 vs. Treatment 2, Treatment 2 vs. Treatment 3, and Treatment 3 vs. Treatment 4) for the ITT population. The Hodges-Lehmann estimators and associated 95% confidence intervals will be calculated for the median differences between Treatment 1 and Treatment 2, Treatment 2 and Treatment 3, and Treatment 3 and Treatment 4. Table 5.3.3.1 provides secondary efficacy results for overall and pairwise comparisons for ADHD-Inattention for the ITT population. Table 5.3.3.2 provides summary statistics for ADHD-Inattention for the restricted ITT population.

Listing 5.3.3.1 provides ADHD-Inattention data for the ITT population.

5.3.4 SNAP-IV Subscale: ADHD-Hyperactivity/Impulsivity

The changes from baseline in the ADHD-Hyperactivity/Impulsivity ratings at each post-baseline visit and endpoint will be compared among treatment groups using Kruskal-Wallis test (for the overall comparisons) and Wilcoxon rank-sum test (for the pairwise comparisons of Treatment 1 vs. Treatment 2, Treatment 2 vs. Treatment 3, and Treatment 3 vs. Treatment 4) for the ITT population. The Hodges-Lehmann estimators and associated 95% confidence intervals will be calculated for the median differences between Treatment 1 and Treatment 2, Treatment 2 and Treatment 3, and Treatment 3 and Treatment 4. Table 5.3.4.1 provides secondary efficacy results for overall and pairwise comparisons for ADHD-Hyperactivity/Impulsivity for the ITT population. Table 5.3.4.2 provides summary statistics for ADHD-Hyperactivity/Impulsivity for the restricted ITT population.

Listing 5.3.4.1 provides ADHD-Hyperactivity/Impulsivity data for the ITT population.

5.3.5 SNAP-IV Subscale: ADHD-Combined Scale

The changes from baseline in the ADHD-Combined Scale ratings at each post-baseline visit and endpoint will be compared among treatment groups using Kruskal-Wallis test (for the overall comparisons) and Wilcoxon rank-sum test (for the pairwise comparisons of Treatment 1 vs. Treatment 2, Treatment 2 vs. Treatment 3, and Treatment 3 vs. Treatment 4) for the ITT population. The Hodges-Lehmann estimators and associated 95% confidence intervals will be calculated for the median differences between Treatment 1 and Treatment 2, Treatment 2 and Treatment 3, and Treatment 3 and Treatment 4. Table 5.3.5.1 provides secondary efficacy results for overall and pairwise comparisons for ADHD-Combined Scale for the ITT population. Table 5.3.5.2 provides summary statistics for ADHD-Combined Scale for the restricted ITT population.

Listing 5.3.5.1 provides ADHD-Combined Scale data for the ITT population.

5.4 EXPLORATORY ANALYSES

5.4.1 SNAP-IV: ODD Subscale

The changes from baseline in the ODD subscale ratings at each post-baseline visit and endpoint will be compared among treatment groups using Kruskal-Wallis test (for the overall comparisons) and Wilcoxon rank-sum test (for the pairwise comparisons of Treatment 1 vs. Treatment 2, Treatment 2 vs. Treatment 3, and Treatment 3 vs. Treatment 4) for the ITT population. The Hodges-Lehmann estimators and associated 95% confidence intervals will be calculated for the median differences between Treatment 1 and Treatment 2, Treatment 2 and Treatment 3, and Treatment 3 and Treatment 4. Table 5.4.1.1 provides exploratory analysis results for overall and pairwise comparisons for ODD subscale for the ITT population. Table 5.4.1.2 provides summary statistics for ODD subscale for the restricted ITT population.

Listing 5.4.1.1 provides ODD subscale data for the ITT population.

